13.6.27 HIV Risk-Taking Behavior Scale (HRBS)

The HRBS is assessed by interview of the subject's engagement in activities that increase the likelihood of contracting HIV. Study personnel are not to offer interpretations of the questions.

13.6.28 Cognitive Battery

This battery of tests is designed to evaluate memory, attention, perceptual speed, and aspects of executive function. Tests have been selected for ease of administration, length, and sensitivity to the deficits found with stimulant abusers (Simon et al, 1999). These assessments will be collected once during the screening/baseline period and at treatment discharge. Each participant will be tested twice on all of the tests with the exception of the Repeated Memory Test (RMT). RMTs are tests that show an effect of repeated administration (Basso, 1999). Two forms of the RMT will be administered.

The participants are shown the RMT memory cards, then given the Trails A & B, then the digit symbol. At this point 10 minutes have passed and they are given the recall, the recognition test and the Stroop. The D2 test of Attention takes an additional 8 minutes. The total time to administer the battery is about 25-30 minutes.

Trail Making A, B. The Trail Making tests tap attention, sequencing, psychomotor speed, and mental flexibility. Trail Making A requires the participant to connect 25 numbers, randomly arranged on a page, in proper order by drawing lines between them. Test B consists of 25 alternating letters and numbers. The participant connects the items (e.g. 1,A,2,B,3,C) by drawing lines. The dependent measure is time (Reitan, 1958; Giovagnoli, 1996).

WAIS-R Digit Symbol sub-test. Digit Symbol sub-test, (Wechsler, 1981) is a measure of psychomotor speed and manipulation of information. The participant is given 90 seconds to fill in the symbols that correspond to a page of numbers using a key with nine numbers and nine corresponding meaningless geometric symbols.

Stroop. Stroop measures selective attention and the ability to ignore irrelevant information by measuring the ease with which a person can conform to changing demands suppress a habitual response in favor of an unusual one (Golden, 1978; Stroop, 1935; MacLeod, 1991).

Repeated Memory Test (RMT). RMT is a test of recall and recognition for pictures and words. Stimuli are controlled for frequency, familiarity, word length and picture complexity and the test provides a measure of source memory and intrusions (Simon, 1999). Two forms of the RMT will be administered. The two forms are equivalent for frequency, word length, picture complexity, and familiarity and have been used in repeated testing with over 500 stimulant abusers and controls without testing effects.

d2 Test of Attention. The d2 test is a concise measure of selective attention and mental concentration. It measures processing speed, rule compliance, and quality of performance in response to the discrimination of similar visual stimuli.

13.6.29 End of Trial Form

If the potential subject screen fails, complete the End of Trial form documenting the screen fail. In addition, during the treatment termination interview, all data relevant to subject's termination: reason for termination; date of final visit; and study day of final visit will be collected.

13.6.30 Treatment Compliance

Treatment compliance will be monitored by recording the amount of investigational agents taken by each subject at each treatment and recorded on a form weekly. The timeline followback method will be used to assist the subject in reporting of the amount of tablets taken between clinic visits. The timeline followback will be administered by the research staff three times a week and reviewed weekly by a physician. On each and all clinic visits (i.e. 3 times per week), self-reports of medication use since the last clinic visit will be recorded on the Treatment Compliance Study Drug Form. Compliance with CBT will be monitored by recording the length of time the subject spent in attendance at each therapy session and recorded on a form for each visit.

13.6.31 Follow-up Questionnaire

The Follow-up Questionnaire will document the information collected at the 30-day follow-up interview including if contact was made with the subject or documenting the subject's death. In addition, the form asks questions regarding the subject's drug use, and current treatment for drug and alcohol abuse.

13.6.33 Timeline Follow-back

Detailed histories of methamphetamine and alcohol use over the past 30 days prior to screening will be obtained using the timeline follow-back method. The timeline followback method was described and validated by Sobell *et al.*, (1986) for reporting alcohol use. It has also been found to be a reliable method for assessing the history of psychoactive substance use in drug-abusing

populations (Fals-Stewart *et al.*, 2000). In addition, this method will be applied to counting tablet usage reported by the subject for treatment compliance determinations.

14 REGULATORY AND REPORTING REQUIREMENTS

14.1 FDA FORM 1572

The investigator at each study site will sign a Statement of Investigator (FDA Form 1572) prior to initiating this study.

14.2 IRB APPROVAL

Prior to initiating the study, the investigator at each study site will obtain written IRB approval to conduct the study. Should changes to the study protocol become necessary, protocol amendments will be submitted in writing to the IRB by the investigator for IRB approval prior to implementation. In addition, IRBs will approve all advertising materials used for subject recruitment and any educational materials (e.g., HIV/AIDS Education, Appendix II) given to the subject. Annual reports and progress reports will be submitted to the IRB annually or at a frequency requested by the IRB.

14.3 INFORMED CONSENT

A two-part informed consent form will be used. All potential candidates for the study will be given a current copy of the Informed Consent Form to read. The investigator, sub-investigators, or study physician or designated staff at each site will explain all aspects of the study in lay language and answer all of the candidate's questions regarding the study. If the candidate desires to participate in the study, s/he will be asked to sign the Informed Consent. No study procedure will be performed prior to signing Informed Consent. Subjects who refuse to participate or who withdraw from the study will be treated without prejudice. The consent will be for the study with part one being consent to start screening procedures that do not include medical assessments such as blood collection and ECG. When an investigator has explained the study and answered the potential participant's questions, part two of the consent form will be signed and the remaining medical procedures to be conducted during screening may be performed.

14.4 DRUG ACCOUNTABILITY

Upon receipt, the investigator/pharmacist or a licensed designate is responsible for taking inventory of the investigational agents(s). A record of this inventory must be kept and usage must be documented. Any unused or expired investigational agent(s) shall be returned to the sponsor or Murty Pharmaceuticals unless otherwise instructed.

14.5 OUTSIDE MONITORING

Data and Safety Monitoring Board: Safety data will be reviewed by a data and safety monitoring board that will meet after the first 50 subjects have been enrolled and again at the end of the study. Additional meetings may be held on an *ad hoc* basis. The board will be unblinded to subjects' actual treatment assignments for the safety data. Reports from the DSMB will be sent

to the project principal investigator and site principal investigators for transmission to their respective IRBs, in accordance with NIH policy.

Medical Monitor: An independent medical monitor will be appointed for the study. The medical monitor will be responsible for establishing concurrence with the investigator on the severity of any SAEs, the relatedness to the study treatments, and for determining if the SAE should be reported to the FDA in a 7 or 15 day expedited report or an annual report. The medical monitor will also be responsible for tracking and assessing trends in the SAEs reported.

Clinical Monitors: All investigators will allow representatives of the sponsor to periodically audit, at mutually convenient times during and after the study, all CRFs and corresponding source documents for each subject. These monitoring visits provide the sponsor with the opportunity to evaluate the progress of the study and to inform the sponsor of potential problems at the study sites. The monitors will assure that submitted data are accurate and in agreement with source documentation; verify that investigational medications are properly stored and accounted for, verify that subjects' consent for study participation has been properly obtained and documented, confirm that research subjects entered into the study meet inclusion and exclusion criteria, and assure that all essential documentation required by good clinical practices guidelines are appropriately filed.

Monitors will conduct a site initiation visit prior to the start of the study. At this visit, they will assure that proper study-related documentation exists, assist in training investigators and other site personnel in study procedures and compliance with good clinical practice guidelines and FDA regulations, confirm receipt of study supplies, and assure that acceptable facilities are available to conduct the study.

Routine monitoring visits by the sponsor's representatives will be scheduled at appropriate intervals but more frequently at the beginning of the study. At these visits, the monitors will verify that study procedures are being conducted according to the protocol guidelines. At the end of the study they will advise on storage of study records and return of unused investigational agents. All sites should anticipate visits by NIDA, the IND sponsor, and the FDA.

Study Coordination: The Coordinating Center (UCLA) will oversee activities of the other investigational sites where the protocol is being conducted. The Coordinating Center staff, in collaboration with NIDA and the data-coordinating center, contracted by NIDA, organize and manage all meetings to facilitate the study, provide training, and offer technical assistance. The Coordinating Center also serves as liaison between, NIDA, the other participating sites, and the data-coordinating center responsible for monitoring the study.

14.6 ADVERSE EVENTS REPORTING

In accordance with FDA reporting requirements, all AEs occurring during the course of the clinical trial will be collected, documented, and reported by the principal investigator or sub-investigators according to the specific instructions detailed in this section of the protocol and Appendix III. The occurrence of AEs will be assessed at each study visit and an AE CRF completed weekly.

An AE is defined as any reaction, side effect, or untoward event that occurs during the course of the clinical trial, whether or not the event is considered medication-related or clinically significant. For this study, AEs will include events reported by the subject, as well as clinically significant abnormal findings on physical examination or laboratory evaluation. A new illness, symptom, sign or clinically significant clinical laboratory abnormality or worsening of a pre-existing condition or abnormality is considered an AE. Stable chronic conditions, such as arthritis, which are present prior to clinical trial entry and do not worsen are not considered AEs. All AEs must be recorded on the AE Form. The AE Form is also used to record follow-up information for unresolved events reported on previous visits.

Each week, a study investigator must review the AE Form completed for the previous week for any events that were reported as continuing. All AEs, including clinically significant abnormal findings on laboratory evaluations, regardless of severity, will be followed by study investigators until satisfactory resolution. AEs should be reported up to 4 weeks following completion of, or termination from treatment.

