- 10. Be mandated by the court to obtain treatment for methamphetamine-dependence where such mandate required the results of urine toxicology tests to be reported to the court.
- 11. In the opinion of the investigator, be expected to fail to complete the study protocol due to probable incarceration or relocation from the clinic area.
- 12. Be undergoing HIV treatment with antiviral and/or non-antiviral therapy.
- 13. Have AIDS according to the current CDC criteria for AIDS-MMWR 1999; 48 (no, RR-13:29-31).
- 14. Have CD4 (+) T-lymphocytes blood counts <500 cells/mm³.
- 15. Have known or suspected hypersensitivity to bupropion.
- 16. Be using bupropion or any medication that could interact adversely with bupropion, within the following times of beginning of administration of bupropion based on the longest time interval of A, B, and C, below or as otherwise specified:

- A) Five half lives of other medication or active metabolite(s), whichever is longer;
- B) Two weeks; or
- C) Interval recommended by other medication's product labeling.

Medications that fall into this category include:

- a. Bupropion (Wellbutrin[®], Zyban[®]) used during the past 30 days
- b. All antidepressants
- c. Neuroleptics
- d. Systemic corticosteroids
- e. Xanthines, i.e., theophilline, theophilline sodium glycinate and aminophylline
- 17. Have participated in any experimental study within 8 weeks (the nature of excluded studies may be discussed with NIDA investigators).
- 18. Be pregnant or lactating.
- 19. Have clinically significant laboratory values (outside of normal limits), in the judgment of the investigator (Appendix I).
- 20. Have active tuberculosis (positive tuberculin test and confirmatory diagnostic chest x-ray).
- 21. Have a diagnosis of adult (i.e., 21 years or older) asthma, or chronic obstructive pulmonary disease (COPD), including those with a history of acute asthma within the past two years, and those with current or recent (past 3 months) treatment with inhaled or oral beta-agonist or steroid therapy (because of potential serious adverse interactions with methamphetamine).

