12.7 FOLLOW-UP (WEEK 16)

Subjects will be asked to return to the clinic 30-days after completion of treatment. During the follow-up interview (week 16 or 4 weeks after the premature treatment discharge date), the

subject will be asked to provide a urine specimen for methamphetamine/creatinine and urine drug screen and provide a self-report for use of methamphetamine, cocaine, opiates, alcohol, cigarette smoking, and marijuana. The subject will also be asked to provide any current treatments for drug or alcohol abuse. Concomitant medications and adverse events will be assessed, and the subject will complete the follow-up form. If it is not possible to arrange for the subject to return to the clinic, then they should be telephoned and asked to provide a current self-reported methamphetamine and other drug use, current treatment for drug or alcohol abuse. Concomitant medications and adverse events will be assessed over the telephone as well as the follow-up form. If a subject cannot be contacted directly, attempts will be made to reach the individual(s) previously identified by the subject as a contact source.

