13.5 ASSESSMENTS AT FINAL FOLLOW-UP (WEEK 16)

Subjects will undergo the following assessments 4 weeks after completion of treatment:

- 1. Urine methamphetamine and creatinine
- 2. Urine toxicology screen (urine specimen sent to NWT for analysis)
- 3. Urine toxicology screen using an onsite testing device
- 4. SUR
- 5. AEs
- 6. Concomitant medications
- 7. Follow-up questionnaire

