14.7 SERIOUS ADVERSE EVENTS

Each adverse event or reaction will be classified by the study investigator as serious or nonserious. Based on the seriousness of the adverse event or reaction appropriate reporting procedures will be followed. The International Conference on Harmonization (ICH) Guideline for Industry: Clinical Safety Data Management: Definitions and Standards for Expedited Reporting, ICH-E2A March 1995, as implemented by the U.S. Food and Drug Administration defines serious adverse event (SAE) or reaction as any untoward medical occurrence that at any dose:

- results in death;
- is life-threatening; (NOTE: The term "life-threatening" in the definition of "serious" refers to an event in which the patient was at risk of death at the time of the event; it does not refer to an event which hypothetically might have caused death if it were more severe.)
- requires inpatient hospitalization or prolongation of existing hospitalization;
- results in persistent or significant disability/incapacity; or
- is a congenital anomaly/birth defect.

An unexpected event is one that is not described with respect to nature, severity, or frequency in the current Investigator's Brochure or product package insert.

Any SAEs due to any cause, that occur during the course of this investigation, whether or not related to the investigational agent, must be reported within 24-hours by telephone to: the Study Medical Monitor, the NIDA Project Officer/Project Manager, the UCLA Coordinating Center, and the investigator-sponsor as follows:

NIDA Medical Monitor: [name]. [name]

NIDA Project Officer: [name], M.S., [name]

NIDA Project Manager: [name], RN, BC, M.S. [name]

Coordinating Center Principal Investigator: [name]., [name]

The telephone report is to be followed by submission of a completed SAE Form with demographic information and a narrative explanation of the event. Attached to the SAE Form should be photocopies of the AE Form, the Concomitant Medication Form, and the Medical History Form from the subject's CRFs. All serious medical events are also to be reported to the responsible IRB according to local regulatory requirements. All participating investigators will be notified of any serious and unexpected AE requiring submission to the FDA in an IND safety report from the investigator-sponsor.

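### Birth defect is a listed SAE, but AE reporting closes 4 weeks after treatment and no text requires a pregnancy to be reported or followed, or study agent to stop on a positive test

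*Protocol*

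**What the plan says.** - **Serious events (14.7).** One of the criteria for a serious event is that it "is a congenital anomaly/birth defect". The 24-hour reporting duty covers "Any SAEs due to any cause, that occur during the course of this investigation, whether or not related to the investigational agent". No separate, longer window is given for serious events.
- **Reporting window (14.6).** "AEs should be reported up to 4 weeks following completion of, or termination from treatment".
- **AE definition and follow-up (14.6).** An AE is "any reaction, side effect, or untoward event that occurs during the course of the clinical trial", and clinically significant laboratory abnormalities count. AEs, "regardless of severity, will be followed by study investigators until satisfactory resolution". Pregnancy is not named here or in Appendix III.
- **Last contact (12.7, 13.5).** "Subjects will be asked to return to the clinic 30-days after completion of treatment", or 4 weeks after premature discharge. The assessment list opens "Subjects will undergo the following assessments 4 weeks after completion of treatment" and has seven items, none of them a pregnancy test or question.
- **Pregnancy testing (synopsis, 13.3, 13.4, 13.6.13).** Tests are at screening, weeks 4 and 8, and termination. A pregnancy form is completed for every subject; what it records about outcome is not described.
- **Action on pregnancy (9.2, 12.12.1).** Under exclusion criterion 18 a participant must not "Be pregnant or lactating". On study, a positive test is one of several reasons for which an investigator may terminate a subject.

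**The concern.** The protocol treats a birth defect as serious but closes its reporting window, and its last scheduled contact, long before a term birth could follow a conception on treatment. Whether the event comes to light depends on how a site classifies a positive test, or on the subject getting in touch.

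The second strand concerns dosing. Pregnancy keeps a woman out of the trial, yet after randomization the decision to stop study agent is left to the investigator. The same section 12.12.1 does write a mandatory stop elsewhere: benzodiazepine or barbiturate positives that persist more than 3 weeks after a warning lead to discontinuation of bupropion. Pregnancy has no equivalent rule.

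What is at stake is subject and fetal safety and the completeness of the safety record. Alpha, power and the treatment comparison are not touched.

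**Working it through.** **1. When the window closes.** Treatment lasts 12 weeks and the window adds 4, so it closes at 12 + 4 = week 16 for a completer, which matches the week 16 visit. Stopping at week 4 or week 8 closes it at week 8 or week 12. Section 12.7 puts the visit at 30 days rather than 28, a two-day difference that changes nothing below.

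**2. When a term birth would occur.** Assumption, not in the documents: term birth at 37 to 42 weeks' gestation, which is 35 to 40 weeks after conception.

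| Conception | Birth (study week) | Weeks after week 16 |
|---|---|---|
| Week 0 | 35 to 40 | 19 to 24 |
| Week 4 | 39 to 44 | 23 to 28 |
| Week 8 | 43 to 48 | 27 to 32 |
| Week 12 | 47 to 52 | 31 to 36 |

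For conception at week c and treatment end at week t, with 0 ≤ c ≤ t ≤ 12, the gap is (c + 35 to 40) − (t + 4) = (31 to 36) − (t − c). Its minimum is 31 − 12 = 19 and its maximum is 36 − 0 = 36, so early terminators lie in the same range. A birth 6 weeks before a 38-week post-conception term (32 weeks after conception) gives 28 − (t − c), which is 16 to 28 weeks. It is still outside the window.

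**3. How many conceptions to expect.** The documents give no pregnancy rate; 5% to 15% a year is assumed.
- Women: 0.30 × 150 = 45, taking the recruitment aim of at least 30% (section 9) as the share. About 22.5 would be on bupropion.
- Mean dosing time, spreading the 46%-50% dropout of section 15.7 evenly over 12 weeks: (1 − d) × 12 + d × 6 = 9.24 weeks at d = 46%, 9.12 at 48% and 9.00 at 50%.
- Bupropion-exposed conceptions at d = 48%: 22.5 × 0.05 × 9.12/52 = 0.20, and 22.5 × 0.15 × 9.12/52 = 0.59.
- Both arms during dosing: 45 × (0.05 to 0.15) × 9.12/52 = 0.39 to 1.18.
- Both arms including the 4 weeks after: 45 × (0.05 to 0.15) × 13.12/52 = 0.57 to 1.70.

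Because 30% is a floor, the figures scale with the share of women. At the 15% rate the bupropion figure reaches one only at about 0.30/0.59 = 51% women.

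**4. Dosing days that could follow a positive test.** Week 4 starts on day 22 and week 8 on day 50. Of 84 dosing days, counting the test day, 84 − 22 + 1 = 63 or 84 − 50 + 1 = 35 remain. These are upper limits, reached only if the investigator continues agent and the subject stays.

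**5. Late conceptions.** Assume a urine test turns positive 10 to 14 days after conception. Conceptions in the last 10 to 14 of 84 dosing days would test negative at termination: 10/84 = 12% to 14/84 = 17% for completers, if conceptions are spread evenly. The week 16 list does not ask about them.

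**The case against.** The strongest reply is that nothing here contradicts anything else. The birth-defect item comes from the ICH definition of serious, which classifies events and does not promise surveillance to delivery. That stands: this is a reporting limit that leaves a listed criterion with no route to capture, not a conflict between two statements.

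A reader might infer that a site following the text is bound to miss a defect. The documents do not support that. A positive test can reasonably be logged as an untoward event or a clinically significant laboratory abnormality, and 14.6 then requires follow-up to resolution. A subject may volunteer the outcome, and AEs are assessed at week 16 with an open question (13.6.18). If a subject is terminated because of pregnancy, the reason is recorded on the End of Trial form (13.6.29). The 24-hour duty might also be read to reach a later birth. But none of these requires a pregnancy to be reported or sets up a contact at which its outcome would be learned, and under 12.6 staff stop making contact once a subject says she is leaving the study.

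A reader might also infer that the protocol endorses dosing through a known pregnancy. It does not. A positive test is a named termination reason, and termination ends dosing after a 3-day taper (11.1). The permissive verb governs the whole list, including danger to self or others, and section 12.9 separately makes discontinuation mandatory for that item. For pregnancy, however, no companion rule appears, so the decision remains discretionary.

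It is also fair that inclusion criterion 7 requires a negative test and agreed contraception or abstinence, and that the assumed pregnancy rate is not adjusted for this. The operations manual, the contents of the pregnancy form and the consent pages are not visible and could hold a follow-up procedure. The protocol text does not point to one.

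**Conclusion.** The point holds as a patient-safety gap that should be closed, with small expected numbers. With gestation assumed at 37 to 42 weeks, no term birth from an on-study conception can fall inside the reporting window; this does not depend on the pregnancy rate. A defect could be missed unless the site logs and follows the pregnancy or the subject reports it. Stopping study agent on a positive test is discretionary.

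Under the assumed rate and 30% women, fewer than one bupropion-exposed conception is expected, and birth defects would be a small fraction of that. The case rests on what the protocol should require of sites, not on a large expected count. Efficacy inference is unaffected.

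**What to change.** - **12.12.1:** require study agent to stop on a confirmed positive pregnancy test, with the taper as the medical monitor directs. CBT and scheduled assessments continue under 12.6.
- **14.6 and 14.7:** require any pregnancy detected from first dose through the week 16 contact to be reported to the medical monitor and, with the subject's consent and as an exception to the cease-contact rule in 12.6, followed by telephone to its outcome. State that the birth-defect criterion applies regardless of the 4-week limit.
- **13.5:** add a pregnancy question for women. It also works when the follow-up is done by telephone.

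The cost is protocol and consent wording, one question, and telephone contacts for the zero to two pregnancies expected across both arms, running up to about 36 weeks past the current window for a conception on treatment. The locator form (13.6.1) already collects contact details. With 46%-50% dropout, some pregnancies would still be lost to follow-up.
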